8.3. Safety Analyses

8.3.1. Overview of Planned Analyses

The safety analyses will be based on the Safety population.

Table 6 provides an overview of the planned analyses with further details of data displays being presented in [Appendix 14: List of Data Displays](#).

Table 6 Overview of Planned Safety Analyses

Endpoints	Observed				Change from Baseline			
	Summary		Individual		Summary		Individual	
	T	F	F	L	T	F	F	L
Adverse Events								
All AEs	Y			Y				
Treatment-Emergent AEs	Y			Y				
Relationship of AEs to Study Drug	Y			Y				
AEs by Maximum Intensity	Y			Y				
Most Common AEs	Y			Y				
Serious AEs	Y			Y				
AEs and SAEs Leading to Treatment Discontinuation	Y			Y				
Fatal AEs and non-fatal SAEs	Y			Y				
AEs of special interest	Y			Y				
Severe, documented symptomatic, and asymptomatic hypoglycemic events in 3-month	Y							
Incidence of hypoglycemic events (in total and by each category as defined by the American Diabetes Association criteria)	Y							
Incidence of daytime hypoglycemia (in total and by category), and nocturnal hypoglycemia (in total and by category)	Y							
Incidence of hypoglycemia with blood glucose <56 mg/dL (<3.1 mmol/L), regardless of symptoms	Y							
Clinical Laboratory	Y	Y		Y	Y	Y		Y
Vital Signs	Y	Y		Y	Y	Y		Y
Electrocardiogram (ECG)	Y	Y		Y	Y			Y

NOTES :

- T = Table, F = Figure, L = Listing, Y = Yes display generated.
- Stats Analysis = Represents TFL related to any formal statistical analyses (i.e. modelling) conducted.
- Summary = Represents TFL related to any summaries (i.e. descriptive statistics) of the observed raw data.
- Individual = Represents FL related to any displays of individual subject observed raw data.

Following review of the data, additional analyses maybe conducted to further support the evaluation and interpretation of the data.

8.3.2. Adverse Events

All AEs will be coded using MedDRA which will be updated whenever available throughout the life of the study. Adverse events will be categorized by their occurrence in regard to therapeutic phase (pre-therapy, on-therapy, or post-therapy) as defined in [Appendix 4](#). Adverse events will be summarized in various subsets by treatment group. An overview summary of the number and percentage of subjects with any AE, the total number of AEs recorded, and the overall AE density and incidence rate for on-therapy AEs will be provided by treatment group. The overview will also summarize SAEs, treatment-related AEs, AEs by maximum intensity, and AEs by therapy phase.

Summaries of the number and percentage of subjects with any treatment-emergent AEs (TEAEs), related AEs, AEs leading to treatment discontinuation or withdrawal from study, SAEs, fatal AEs etc, will be provided. Adverse events will also be summarized by maximum intensity (mild, moderate, and severe).

Except summaries for serious AEs, AEs leading to withdrawal from treatment or pre-therapy AEs, all other AE summaries do not include hypoglycemic events, unless otherwise specified.

All AEs will be listed in a subject data listing.

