4.5. Withdrawal Criteria

Every effort should be made to keep subjects in the study. The reasons for subjects not completing the study will be recorded.

The following **will** require withdrawal from the study:

- AE, which, in the opinion of the investigator precludes effective participation of the subject or poses a safety concern
- Elevation of liver function test results meeting any of the liver stopping criteria (see Section 6.3.6)
- Severe allergic/hypersensitivity reaction that is considered by the investigator to be attributable to randomized study medication or without a likely alternative etiology (see Section 6.3.9.3)
- Confirmed acute or chronic pancreatitis (see Section 6.3.9.4)
- Confirmed medullary thyroid cancer (see Section 6.3.9.6)
- Recurrent severe hypoglycemia or recurrent nocturnal hypoglycemia during the Treatment Period posing a potential risk to the subject, as judged by the investigator
- Pregnancy or intention of becoming pregnant
- Major protocol deviation if withdrawal from the study is mandated by the medical monitor (the investigator should discuss the protocol deviation with the medical monitor before withdrawing study medication)
- GSK-defined Sentinel Event. The medical monitor will advise the investigator if an SAE meets the criteria of a true Sentinel Event (e.g., without a clear alternate etiology) for which withdrawal is required (see Section 6.3.7.3)

In addition, a subject may be withdrawn from the study for the following reasons:

- FPG >270 mg/dL (15.0 mmol/L) at least 8 weeks after randomization on 3 consecutive days (by blood glucose meter), which is confirmed by a central laboratory (to be done within 2 weeks of the home glucose monitoring). Continuation of the subject will be at the discretion of the investigator after consultation with the medical monitor
- Lost to follow-up
- Study closed/terminated or investigator site closed (where subject transfer to another site is not possible)
- Subject decision (reason to be documented in the electronic case report form [eCRF], if specified by the subject)
- Investigator discretion

Note: Use of a prohibited medication constitutes a protocol deviation. Continuation of the subject in the study will be discussed with the medical monitor, and the decision of continuation or withdrawal will be documented.

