Should a subject fail to attend the clinic for a required study visit, the site should attempt to contact the subject and reschedule the missed visit as soon as possible. The site should also counsel the subject on the importance of maintaining the assigned visit schedule and ascertain whether or not the subject wishes to and/or should continue in the study based on previous noncompliance. In cases where the subject does not return for the

rescheduled visit or cannot be reached to reschedule the missed visit, the site should make every effort to regain contact with the subject (3 telephone calls and if necessary a certified letter to the subject's last known mailing address) so that they can appropriately be withdrawn from the study. These contact attempts should be documented in the subject's medical record. Should the subject continue to be unreachable, then and only then will he/she be considered to have withdrawn from the study with a primary reason of "Lost to Follow-up." For all other subjects withdrawing from the study, an alternative reason for discontinuation should be recorded in the eCRF.

The half-life of albiglutide is approximately 5 days, and significant therapeutic concentrations can persist for 3 to 4 weeks after discontinuation. Therefore, the investigator should use caution when prescribing treatment after the withdrawal of active study medication, taking into consideration the long half-life of albiglutide. Thereafter, postwithdrawal treatments may be modified over time, as needed, at the investigator's discretion.

Study medication withdrawal will require withdrawal from the study. Withdrawn subjects will not be replaced.

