8.3.2.1. General Adverse Events Summaries

Summaries of the number and percentage of subjects with AEs and the total number of AEs will be provided by treatment group overall and at the SOC and PT level for the following time periods:

- 1) On-therapy and post-therapy combined period
- 2) Pre-therapy (includes hypoglycemia events)
- 3) On-therapy
- 4) Post-therapy

In addition, on-therapy Adverse events will be presented by time intervals of onset (<=12 weeks, >12 - <=26 weeks) and by treatment group; the on-therapy non-serious AEs will be summarized by treatment group.

An additional on-therapy AE summary will also be provided following government clinical register format; these summaries will include the AEs of hypoglycemia event.

A by-subject listing of all AEs will also be presented.

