11.14.6. Safety Tables

Safety : Tables					
No.	Population	IDSL / TST ID / Example Shell	Title	Programming Notes	Deliverable [Priority]
Exposure to Treatment					
3.01	Safety		Exposure to Treatment		
Treatment Compliance					
3.02	Safety		Treatment Compliance		
Adverse Events					
3.11	Safety		Overview of Adverse Events		
3.12	Safety		All On-therapy and Post-therapy Adverse Events		
3.13	Safety		Pre-therapy Adverse Events		
3.14	Safety		On-therapy Adverse Events		
3.15	Safety		Most Common On-therapy Adverse Events		
3.16	Safety		Post-therapy Adverse Events		
3.17	Safety		On-Therapy Adverse Events and the Information on Relation to Treatment		
3.18	Safety		On-therapy Adverse Events by Time of Onset With 12-Weeks Intervals		
3.19	Safety		On-therapy Non-serious Adverse Events		
3.20	Safety		On-Therapy Non-serious Adverse Events with Incidence of Preferred Term >=5% in Any Treatment Group and the Information on Relation to Treatment		
3.21	Safety		On-therapy and Post-therapy Adverse Events Related to Individual Study Treatment		
3.22	Safety		On-therapy Treatment-related Adverse Events		

Safety : Tables					
No.	Population	IDSL / TST ID / Example Shell	Title	Programming Notes	Deliverable [Priority]
3.23	Safety		Post-therapy Treatment-related Adverse Events		
3.24	Safety		On-therapy and Post-therapy Treatment-related Adverse Events		
3.31	Safety		On-therapy and Post-therapy Adverse Events by Maximum Intensity		
3.32	Safety		On-therapy Adverse Events by Maximum Intensity		
3.33	Safety		Post-therapy Adverse Events by Maximum Intensity		
3.34	Safety		On-therapy and Post-therapy Adverse Events by Maximum Intensity		
3.41	Safety		Pre-therapy Serious Adverse Events		
3.42	Safety		On-therapy Serious Adverse Events		
3.43	Safety		On-Therapy Serious Adverse Events and the Information on Relation to Treatment		
3.44	Safety		Post-therapy Serious Adverse Events		
3.45	Safety		On-therapy Treatment-related Serious Adverse Events		
3.46	Safety		Post-therapy Treatment-related Serious Adverse Events		
3.47	Safety		On-Therapy Fatal Serious Adverse Events and the Information on Relation to Treatment		
3.48	Safety		On-Therapy Non-fatal Serious Adverse Events and the Information on Relation to Treatment		
3.51	Safety		On-therapy Adverse Events Leading to Permanent Discontinuation of the Randomized Study Drug		
3.52	Safety		On-therapy Adverse Events Leading to Withdrawal from Study		
AE of Special Interest					

Safety : Tables					

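### Read literally, the SAP's hypoglycemia exclusion leaves hypoglycemia out of Table 3.52 (AEs leading to study withdrawal) but keeps it in Table 3.51 (AEs leading to stopping study drug)

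*SAP*

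**What the plan says.** SAP 8.3.2 first announces what will be summarized, including "AEs leading to treatment discontinuation or withdrawal from study, SAEs, fatal AEs etc, will be provided". Stopping treatment and leaving the study are named there as two alternatives.

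The same section then sets the hypoglycemia rule: "Except summaries for serious AEs, AEs leading to withdrawal from treatment or pre-therapy AEs, all other AE summaries do not include hypoglycemic events". The sentence closes with a proviso, so that its second half reads in full: "all other AE summaries do not include hypoglycemic events, unless otherwise specified". Later subsections use that closing proviso. SAP 8.3.2.1 and 8.3.2.5 each say that a register-format on-therapy summary will include hypoglycemia, and SAP 8.3.2.1 repeats the pre-therapy exception in its list of periods: "Pre-therapy (includes hypoglycemia events)".

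The table list in SAP 11.14.6 has two separate displays. Table 3.51 covers on-therapy AEs that led to stopping randomized study drug for good. Table 3.52 is "On-therapy Adverse Events Leading to Withdrawal from Study".

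Protocol 4.5 lists, among the criteria that require withdrawal, "Recurrent severe hypoglycemia or recurrent nocturnal hypoglycemia during the Treatment Period posing a potential risk to the subject, as judged by the investigator". It also states: "Study medication withdrawal will require withdrawal from the study". SAP 11.6.3.1 repeats that link.

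**The concern.** The hypoglycemia rule is written by type of summary. It names one of two closely linked withdrawal summaries and leaves the other unnamed. A programmer following the SAP would include hypoglycemia in Table 3.51 and exclude it from Table 3.52, with no footnote to tell the reader that the two rest on different event sets.

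Hypoglycemia is central to this comparison. It is a key secondary endpoint, and Protocol Table 1 calls it the most common adverse effect of insulin. It is also an explicit withdrawal criterion. A table titled as the AEs leading to study withdrawal, but silently lacking this event, can be read on its own as the full count. It would also disagree with its neighbor for no clinical reason.

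**Working it through.** No arithmetic applies, so the check sets the texts side by side.

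1. **What the exempted term means.** SAP 8.3.4 equates withdrawal of active treatment with stopping randomized study drug permanently. SAP 8.3.2 itself names withdrawal from study as something different from treatment discontinuation. In the SAP's own vocabulary, the exception reaches Table 3.51 and not Table 3.52.

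2. **Whether the proviso rescues Table 3.52.** Where the SAP brings hypoglycemia back in, it says so: the register-format on-therapy summary (8.3.2.1), the register-format summary of common non-serious events (8.3.2.5), and the register-format serious-event summaries (8.3.3, already within the serious-AE exception). SAP 8.3.4 describes a summary only for stopping study drug and mentions study withdrawal only for the listing. The entry for Table 3.52 in SAP 11.14.6 carries no note.

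| | Table 3.51 | Table 3.52 |
|---|---|---|
| Subject | AEs leading to stopping study drug | AEs leading to leaving the study |
| Covered by a named exception in 8.3.2 | Yes | No |
| Hypoglycemia expressly included elsewhere | Not needed | No |
| Hypoglycemia counted, read literally | Yes | No |

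3. **Whether the two tables ought to differ.** Protocol 4.5 and SAP 11.6.3.1 make leaving the study follow from stopping treatment. Protocol 4.5.1 supplies the converse: a subject who ends active participation no longer receives randomized medication. The two sets of subjects should largely coincide. They need not match exactly, because SAP 11.6.3.1 says the two reasons are recorded separately in the eCRF.

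4. **Which events are dropped.** The exceptions are defined by kind of summary, not by seriousness of event. Table 3.52 is not a serious-AE summary, so the literal rule removes serious and non-serious hypoglycemia alike. A subject withdrawn for recurrent nocturnal hypoglycemia would be counted in Table 3.51 and be absent from Table 3.52. If the episode was serious, it would also be in the SAE tables, but still not in Table 3.52.

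5. **Where the events remain visible.** They are in Table 3.51; in Table 3.71, which shows hypoglycemic events by withdrawal status (SAP 8.3.5.1); and in the by-subject listings of AEs leading to discontinuation or study withdrawal (SAP 8.3.4; Listings 6 and 7). The exclusion governs summaries, not listings.

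**The case against.** The best reply is that the omission is inferred from wording. Because the design ties stopping treatment to leaving the study, the authors may have meant withdrawal from treatment to cover both. SAP 8.3.4 puts both under one heading, and SAP Table 6 gives them a single row. That intention is plausible, but the SAP does not state it, SAP 8.3.2 uses both terms as alternatives, and two tables are planned. The same short edit settles the matter either way.

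A second reply is that separate handling of hypoglycemia is deliberate (Protocol 8.3.5.2) and that these withdrawals are reported elsewhere. This stands, and it limits the consequence to one table. It does not correct the count in that table.

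Some stronger readings are tempting, but the documents do not support them:

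- *Hypoglycemia is removed from all but three AE summaries.* The proviso and the register-format summaries contradict this.
- *The pre-therapy and on-therapy rows of the AE overview are not comparable because of the rule.* The overview is not a named exception, so its phase rows may all exclude hypoglycemia. No comparison between phases is planned, and the periods differ in length in any case.
- *The shortfall can be sized from the earlier albiglutide-versus-lispro study, with AE withdrawals of 5% on albiglutide and under 1% on lispro.* Those rates concern withdrawal of active treatment, which is what Table 3.51 measures. Neither document gives a count of hypoglycemia withdrawals.
- *The omission falls mainly on the lispro arm and distorts the tolerability comparison.* Protocol 1.2 cites about 1.5- to 2-fold less symptomatic hypoglycemia with albiglutide, which makes the direction plausible. But Protocol Table 1 also says that combining albiglutide with insulin raises the risk, and the withdrawal criterion depends on investigator judgment. With Tables 3.51 and 3.71 available, a distorted comparison does not follow.

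**Conclusion.** The point holds in limited form. As written, the rule in SAP 8.3.2 gives a wrong count in Table 3.52: all hypoglycemia-related study withdrawals are left out, although Table 3.51 includes them and the design makes the two sets of withdrawals largely the same. Severity is low. The number of subjects affected cannot be estimated from the documents and could be zero. No estimate, hypothesis test, power figure or primary analysis changes.

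The conclusion assumes that the SAP is followed literally, that withdrawal from treatment carries the meaning given in SAP 8.3.4, and that no programming note outside these documents brings hypoglycemia into Table 3.52.

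**What to change.** In SAP 8.3.2, extend the second exception so that it reads: AEs leading to withdrawal from treatment or from the study. Tables 3.51 and 3.52 then follow the same hypoglycemia rule. The cost is a few words in the SAP and a matching programming specification for Table 3.52. No new data are needed.

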8.3.2.1. General Adverse Events Summaries

Summaries of the number and percentage of subjects with AEs and the total number of AEs will be provided by treatment group overall and at the SOC and PT level for the following time periods:

- 1) On-therapy and post-therapy combined period
- 2) Pre-therapy (includes hypoglycemia events)
- 3) On-therapy
- 4) Post-therapy

In addition, on-therapy Adverse events will be presented by time intervals of onset (<=12 weeks, >12 - <=26 weeks) and by treatment group; the on-therapy non-serious AEs will be summarized by treatment group.

An additional on-therapy AE summary will also be provided following government clinical register format; these summaries will include the AEs of hypoglycemia event.

A by-subject listing of all AEs will also be presented.

8.3.2.2. Treatment Emergent Adverse Events

TEAEs are defined as any AEs, regardless of relationship to the, randomized study drug (i.e., albiglutide or other study treatments), that occur after the first dose of the

randomized study medication, which is equivalent to on-therapy and post-therapy AEs combined. Summaries of the number and percentage of subjects with TEAEs will be provided by treatment group overall at the SOC and PT level. TEAES will also be further defined as on-therapy or post-therapy AEs for summary purposes.

A by-subject listing of all TEAEs will also be presented.

8.3.2.3. Treatment-Related Adverse Events

Treatment-related AEs will be defined as any AEs that are considered by the investigator to have a reasonable possibility to be related to the study treatment. If a relationship to the study treatment is missing or unknown after the start of treatment it will be assumed, for the purpose of analyses, to be treatment-related.

A summary of the number and percentage of subjects with treatment-related AEs will be displayed. The treatment-related AE data will be categorized and presented in a manner similar to that described above for the general AE summaries for both the on-therapy and post-therapy therapeutic phases.

8.3.2.4. Adverse Events by Maximum Intensity

A summary of the number and percentage of subjects with on-therapy and post-therapy adverse events by intensity (mild, moderate, and severe) will be produced. The data will be sorted and categorized using the method and format described previously.

Subjects who experience the same event several times with different intensity will only be counted once according to the maximum intensity experienced (for that therapeutic phase). AEs with missing intensity will be considered to be severe for the purposes of summarization.

8.3.2.5. Most Common Adverse Events

A summary of most common on-therapy adverse events (>2% total incidence in any treatment arm) by treatment will be produced.

In addition, on-therapy non-serious AEs with proportion of subjects experiencing the AE $\geq 5\%$ among any of the active arms will be summarized by treatment group following government clinical register format; this summary will include AEs of hypoglycemia event.

8.3.3. Deaths and Serious Adverse Events

Serious adverse events (SAEs) will be summarized in a manner similar to that described above for the general AE summaries by treatment group for pre-therapy, on-therapy, and post-therapy therapeutic phases. Treatment-related SAEs will also be summarized separately by treatment group for both the on-therapy and post-therapy therapeutic phases.

SAE, fatal SAE and serious non-fatal AEs will also be summarized following government clinical register format; these summaries will include SAEs of hypoglycemia event.

Summaries and by subject listings of fatal AEs and serious non-fatal AEs will be presented.

8.3.4. Adverse Events Leading to Discontinuation of Investigational Product and/or Withdrawal from the Study

A summary of the number and percentage of subjects with adverse events leading to permanent discontinuation of the randomized study drug (that is, withdrawal of active treatment) will be presented by treatment group for the on-therapy phase.

A by-subject listing of all adverse events leading to permanent discontinuation of study drug/withdrawal from the study will be produced.

8.3.5. Adverse Events of Special Interest

For selected AEs of special interest such as hypoglycemia, the exposure-adjusted event rate, i.e., AE density, will be calculated as the number of events in a given period divided by the total person time on treatment of subjects at risk within the same period; the exposure-adjusted incidence rate will also be calculated as the number of subjects in a given period divided by the total person time on treatment of subjects at risk within the same period. The exposure-adjusted event rate and incidence rate will be expressed as an annualized rate (expected number of events or subjects per 100 person-years).

For any AEs of special interest, if the number of events is limited and does not warrant summary tables, by subject data listings will be provided instead.

8.3.5.1. Hypoglycemic Events

Hypoglycemic events merit special attention in the development and study of drugs for the treatment of T2DM since they are often related to the efficacy of a compound. In order to accomplish this, hypoglycemic event data including supplemental hypoglycemic event information not collected on AE eCRF page are reported on a separate hypoglycemic event eCRF page. However, any hypoglycemic event that meets the criteria for a serious AE will also be included in the serious AE summaries.

Analysis of on-therapy hypoglycemic events will include all AEs coded to the preferred term of 'Hypoglycemia'. For on-therapy hypoglycemic events the number and percentage of subjects with events, the number of events, the incidence rate (per 100 person-years) and AE density (per 100 person-years) by the severity of the event defined by American Diabetes Association [ADA], SAE status, relationship to the investigational product, and withdrawal status will be summarized by treatment group. The events will also be summarized according to intervention provided, action taken with regard to background and anti-hyperglycemic medications and onset week and glucose levels. All hypoglycemic events will be classified as severe, documented symptomatic,

asymptomatic, probable symptomatic, or pseudohypoglycemia per the American Diabetes Association criteria) criteria.

The number of events of hypoglycemia with confirmed home blood glucose monitoring < 3.9 mmol/L and/or requiring third party intervention (i.e., severe, documented symptomatic and asymptomatic hypoglycemic events) in 3 monthly intervals (i.e., from Baseline to Week 12, >Week 12 to Week 26) will be summarized by treatment group. The exposure-adjusted event rate will be compared between treatment groups using a Poisson regression model with offset for the person-year, which will include HbA_{1c} stratum, age (<65 years versus ≥65 years), current use of metformin (metformin use versus no metformin use), and region as covariates.

Incidence (in total and by each category) of hypoglycemia, daytime hypoglycemia, and nocturnal hypoglycemia will be summarized by treatment group. Daytime hypoglycemia is defined as hypoglycemic events with an onset between 06:00 hours and 00.00 hours (inclusive). Nocturnal hypoglycemia is defined as hypoglycemic events with an onset between 00:01 hour and 05:59 hours (inclusive). The incidence of hypoglycemia with blood glucose <56 mg/dL (<3.1 mmol/L), regardless of symptoms, will also be summarized by treatment group.

On-therapy hypoglycemic events over time will be summarized by onset week and plotted for each treatment group.

A by-subject listing of all hypoglycemic events will be produced.

